#### Worst-case principle:

To avoid a potential misclassification of an AE to a vaccination period or to the overall vaccination period, if an imputed start date corresponds to the first of the month or to the first of the year, and matches the month and year of the first or second vaccination date, then the AE will be assigned to the vaccination period with matching month and year. If the AE cannot be assigned to a vaccination period because of a (partially) missing start date then it will be only assigned to the overall vaccination period.

### **3.3.4 General Considerations for AEs**

Medical Dictionary for Regulatory Activities (MedDRA) Version 19.1 will be used for coding of AEs.

#### Duration of an AE will be calculated as follows:

For Unsolicited AEs: expressed in [days]

- End date – start date of AE + 1 day. Note that duration can be calculated even if time of day is missing for either start or end dates, or if time is missing for both.
- In case of partially missing start date (month and/or day missing) or partially missing end date (month and/or day missing), duration will not be calculated.
- In case of an ongoing AE, the duration will not be calculated.

For Solicited AEs: expressed in [days]

- End date of AE – start date of AE + 1, where end date is the last day the symptom is defined as an AE and start date is the first day symptom is defined as an AE (no matter if the AE occurred at every day between first day and last day). In case of an ongoing AE, the duration will not be calculated.

Relative day of onset between vaccination and start of AE will be calculated as follows:

For Unsolicited AEs: expressed in [days]

- Start date of AE – corresponding vaccination date.
- In case of (partially) missing start date no calculation will be done.

For Solicited AEs: expressed in [days]

- The relative day is calculated as the day of first symptom intensity recording > 0.
- Start date of AE – corresponding vaccination date, where start date is the first day a symptom is defined as an AE; vaccination day corresponds to Day 0.

### 3.4. Analysis Variables

#### 3.4.1 Demographic and other Baseline Characteristics

##### Demographics

- Age (years)
- Age Group ( $\geq 55$  to  $< 70 \geq 70$ )
- Gender (male, female)
- Race (White/Caucasian, Black or African American, Asian, American Indian or Alaskan Native, Native Hawaiian or Other Pacific Islander, Other, Missing)
- Ethnicity (Hispanic or Latino, or Not Hispanic or Latino, Missing)
- Height [cm]
- Body weight [kg]
- Body Mass Index (BMI)

##### Other baseline characteristics

- Medical history
- Prior and concomitant medications
- Pre-vaccination AEs pre-existing to vaccination

Demographics tables will be presented by treatment group for the FAS, PPS, and IAS populations. Other baseline characteristics will be summarized by treatment group for the FAS only. Demographics and other baseline characteristics will be presented in separate subject listings.

### 3.4.2 Safety Variables

#### Physical examination (complete examination at Screening Visit and targeted physical examination at V1, V2, V3, V4, EAP, FU1 and FU2 Visits)

(A targeted physical examination, guided by any signs or symptoms previously identified or any new symptoms that the subject has experienced since the last visit, is required at all visits starting at Visit 1 except VS.)

A subgroup of subjects who will provide additional PBMC samples also will have physical examination reported at V1b and V3b.

Only abnormal physical examinations will be listed.

#### Vital signs (at Screening, V1, V2, V3, V4, EAP, FU1 and FU2 Visits)

- Heart rate [beats per minute]
- Systolic and diastolic blood pressure [mmHg]
- Oral body temperature [°C]

The PBMC subgroup also has vital signs reported at V1b and V3b.

Baseline, actual and change from baseline vital sign parameters will be summarized and individual subject listings will be presented.

#### 12-lead electrocardiogram (ECG) (at Screening and if clinically indicated at V2, V4, FU1 and FU2 Visits)

(Additional ECGs will be performed and reported if clinically indicated, or in case any clinically significant cardiac events are present).

- Assessment of ECG (categorized as normal, normal variant, abnormal)
- Interpretation of ECGs assessed as abnormal (categorized as abnormal not clinically significant or abnormal clinically significant)

Screening ECG parameters and overall interpretation will be summarized. Individual subject listings will also be presented.

#### Safety laboratory data (at Screening Visit, V2 and V4 and if clinically indicated at FU1 or FU2 Visits)

The safety laboratory measurements are performed at a central laboratory. Laboratory normal ranges are provided by the central laboratory.

Serum chemistry:

- Total Bilirubin (mg/dL)
- Alkaline Phosphatase (AP) (U/L)

Study specific version: 1.0  
Study specific version Date: 31-May-17

- Aspartate Aminotransferase (AST) (U/L)
- Alanine Aminotransferase (ALT) (U/L)
- Creatinine (mg/dL)
- Sodium (mmol/L)
- Potassium (mmol/L)
- Calcium (mg/dL)
- Troponin I (ng/mL) (at Screening Visit and if clinically indicated at V2, V4, FU1 or FU2 Visits).

For subjects with type II diabetes mellitus HbA1c is assessed at the SCR visit only in case documented HbA1c result within three months prior to SCR is not available.

Hematology:

- Red blood cell count ( $\times 10^6/\mu\text{L}$ )
- Hemoglobin (g/dL)
- Total and differential White Blood Cell count (WBC) ( $\times 10^3/\mu\text{L}$ )
- Platelet count ( $\times 10^3/\mu\text{L}$ )
- Hematocrit (%)
- Mean corpuscular/cell volume (MCV) (fL)
- Mean corpuscular/cellular hemoglobin (MCH) (pg)
- Mean corpuscular hemoglobin concentration (MCHC) (g/dL)
- Red blood cell distribution width (RDW) (%)

Baseline, actual values at each visit, and change from baseline safety laboratory parameters (serum chemistry and hematology) will be summarized and individual subject listings will be presented.

Shift tables will also be presented for serum chemistry and hematology using the categories of Missing, Below Lower Limit of Normal, Normal, and Above Upper Limit of Normal.

#### Pregnancy Test (Screening, V1, V3 and EAP)

A  $\beta$ -human choriogonadotropin (HCG) pregnancy test will be conducted for all WOCBP at SCR Visit, prior to each vaccination and at the individual last active trial phase visit (Visits 1, 3 and EAP). At SCR Visit a serum  $\beta$ -HCG pregnancy test will be performed; all other pregnancy tests will be conducted as urine  $\beta$ -HCG tests.

Pregnancy test results will be presented as individual subject listings for all WOCBP in the study.

#### Virology (Screening)

The following viruses are only evaluated during the screening period for assessment of inclusion/exclusion criteria and at subsequent visits only if clinically indicated:

- HIV antibody test (anti HIV)
- HBsAG
- Hepatitis C antibody test

If appropriate, virology results will be presented as individual subject listings.

#### Respiratory Viral Panel

In case of any symptoms indicating a respiratory tract infection at any time point after the first vaccination a nasal swab will be obtained at scheduled or unscheduled visits to assess if a current RSV infection is underlying. Subjects are instructed to return to the site within 3 days after start of symptoms.

Respiratory viral panel results will be presented as individual subject listings.

#### Solicited local AEs reported in the subject memory aid (at each vaccination, on day of vaccination and during the following 7 days)

- Injection Site Erythema (0 = 0, 1 denotes < 30 mm, 2 denotes  $\geq 30$  - < 100 mm, 3 denotes  $\geq 100$  mm)
- Injection Site Swelling (0 = 0, 1 denotes < 30 mm, 2 denotes  $\geq 30$  - < 100 mm, 3 denotes  $\geq 100$  mm)
- Injection Site Induration (0 = 0, 1 denotes < 30 mm, 2 denotes  $\geq 30$  - < 100 mm, 3 denotes  $\geq 100$  mm)
- Injection Site Pruritus (0 = Absent, 1 = Mild, 2 = Moderate, 3 = Severe)
- Injection Site Pain (0 = Absent, 1 = Painful to Touch, 2 = Painful when limb is moved, 3 = Spontaneously painful / prevents normal activity)

Solicited local AEs will be summarized by maximum intensity and vaccination period (and overall). Individual subject listings for solicited local AEs will also be presented.

#### Solicited general AEs reported in the subject memory aid (at each vaccination, on day of vaccination and during the following 7 days)

Grading of General Symptoms from the Subject's Memory Aid

| MedDRA coded Preferred Term
General AEs | Grade | Maximum Severity  |
|--|--------------|--|
| Body temperature*                                  | 0            | < 99.5°F (< 37.5°C)  |
|  | 1            | ≥ 99.5 – < 100.4°F (≥ 37.5 – < 38.0°C)   |
|  | 2            | ≥ 100.4 – < 102.2°F (≥ 38.0 – < 39.0°C)  |
|  | 3            | ≥ 102.2 – < 104.0°F (≥ 39.0 – < 40.0°C)  |
|  | 4            | ≥ 104.0°F (≥ 40.0°C)   |
| Headache, Myalgia, Nausea, Chills and Fatigue      | 0            | None   |
|  | 1            | Mild: easily tolerated, minimal discomfort and no interference with daily activity |
|  | 2            | Moderate: Some interference with daily activity                                    |
|  | 3            | Severe: Prevents daily activity  |

\*Pyrexia is defined as oral temperature ≥ 100.4°F (≥ 38.0°C).

Solicited general AEs will be summarized by maximum intensity and vaccination period (and overall). Individual subject listings for solicited general AEs will also be presented.

Other safety variables include:

- SAEs

### **3.4.3 Immunogenicity Variables**

Antibody titers (at V1, V1b, V2, V3, V3b, V4, EAP, FU1, FU2)

- Serum RSV-specific antibodies (IgG ELISA)
- Serum RSV-specific antibodies (IgA ELISA)
- Serum RSV-strain A – G protein specific antibodies (IgG ELISA)
- Serum RSV-strain B – G protein specific antibodies (IgG ELISA)
- Serum RSV-strain A specific neutralizing antibodies (PRNT)
- Serum RSV-strain B specific neutralizing antibodies (PRNT)
- Mucosal RSV-specific antibodies ELISA (IgA ELISA)

ELISPOT SFU/1x10^6 PBMC (at V1, V1b, V2, V3b, V4 for PBMC subgroup only)

- IFN-γ RSV Peptide pool (pool F, G(A), G(B), N, M2, RSV virus)
- IL-4 RSV Peptide pool (pool F, G(A), G(B), N, M2, RSV virus)

(Sero)positivity ELISA and PRNT (yes/no) (at V1, V1b, V2, V3, V3b, V4, EAP, FU1, FU2)

- Serum RSV-specific antibodies (IgG ELISA)
- Serum RSV-specific antibodies (IgA ELISA)
- Serum RSV- strain A – G protein specific antibodies (IgG ELISA)
- Serum RSV-strain B – G protein specific antibodies (IgG ELISA)
- Serum RSV-strain A specific neutralizing antibodies (PRNT)

- Serum RSV-strain B specific neutralizing antibodies (PRNT)
- Mucosal RSV-specific antibodies ELISA (IgA ELISA)

Positivity ELISPOT (yes/no) (at V1, V1b, V2, V3b, V4 for PBMC subgroup only)

- IFN- $\gamma$  RSV Peptide pool (pool F, G(A), G(B), N, M2, RSV virus)
- IL-4 RSV Peptide pool (pool F, G(A), G(B), N, M2, RSV virus)

Response ELISA and PRNT (yes/no) (at V1b, V2, V3, V3b, V4, EAP, FU1, FU2)

- Serum RSV-specific antibodies (IgG ELISA)
- Serum RSV-specific antibodies (IgA ELISA)
- Serum RSV-strain A – G protein specific ELISA (IgG ELISA)
- Serum RSV-strain B – G protein specific ELISA (IgG ELISA)
- Serum RSV-strain A specific neutralizing antibodies (PRNT)
- Serum RSV-strain B specific neutralizing antibodies (PRNT)
- Mucosal RSV-specific antibodies ELISA (IgA ELISA)

Response ELISPOT (yes/no) (at V1b, V2, V3b, V4 for PBMC subgroup only)

- IFN- $\gamma$  RSV Peptide pool (pool F, G(A), G(B), N, M2, RSV virus)
- IL-4 RSV Peptide pool (pool F, G(A), G(B), N, M2, RSV virus)

ELISPOT RSV-specific Responder Status (yes/no) (per subject V1b through V4 for PBMC subgroup only)

- IFN- $\gamma$  RSV Peptide pool (pool F, G(A), G(B), N, M2, RSV virus)
- IL-4 RSV Peptide pool (pool F, G(A), G(B), N, M2, RSV virus)

Refer to Section [3.5.7](#) for details of immunogenicity analyses.

#### **3.4.4 Pharmacokinetic Variables**

Not applicable.

#### **3.4.5 Pharmacodynamic Variables**

Not applicable.

### **3.5. Analysis and Presentation of Methods**

#### **3.5.1 Listings and Descriptive Statistics**

All individual data entered in the eCRF and derived data will be listed as measured in the Individual Subject Data Listing.

Study specific version: 1.0  
Study specific version Date: 31-May-17

For all ELISA and PRNT titers descriptive statistics will be based on number of observations (n), Geometric Means, confidence intervals (CI), minimum (Min), median, maximum (Max). Other continuous measurements will be summarized using descriptive statistics (i.e., number of observations (n), arithmetic mean, standard deviation (SD), Min, median, Max and categorical data will be summarized by means of frequency tables (i.e., count and percentages), if not stated otherwise. Unless otherwise stated, the Min and Max will be reported with the same number of decimal places as the individual values are recorded. CIs, Means, Medians, and SD will be reported to one additional decimal place.

Descriptive statistics for the SFU values will be based on both the GMSFU and the median (with associated CI) and Min and Max.

A non-parametric percentile based CI ([Hahn](#) G and Meeker W (1991) *Statistical Intervals: A Guide for Practitioners*, New York: John, 1991) will be placed around the median for each group, using the SAS UNIVARIATE Procedure, i.e.:

```
PROC UNIVARIATE DATA=<dataset_name> CIPCTLDF; VAR SFU; BY GROUP; RUN;
```

Repeated assessments/measurements and unscheduled assessments/measurements will be included in the Individual Subject Data Listing. All tables and listings will be sorted by scheduled visit with unscheduled visits listed in-between scheduled visits (and by subject, if appropriate).

All tables will be presented by treatment groups. Solicited AEs will be presented by treatment and age group ( $\geq 55$  to  $< 70$  and  $\geq 70$  years). For immunogenicity analysis, only PRNT strain A and ELISA IgA will be presented by treatment and age group ( $\geq 55$  to  $< 70$  and  $\geq 70$  years). The remaining ELISA immunogenicity analyses will be presented by treatment group only.

Summary by subject refers to summary of the overall period, e.g., the overall vaccination period, or the ATP. An event will only be counted once during the period.

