## 1.5 Protocol Synopsis

Title	A randomized, single-blind, placebo controlled, dose-ranging Phase II trial in $\geq$ 55 year old adults to evaluate the safety and immunogenicity of the recombinant MVA-BN-RSV vaccine
Clinical phase	Phase II
Sponsor	Bavarian Nordic A/S [name]
Coordinating Investigator	[REDACTED]
Number of sites and Country/ies	up to 16 sites in the USA
Vaccination dose and schedule	
Liquid frozen (LF) suspension of MVA-mBN294B (common name MVA-BN-RSV vaccine), containing a nominal titer of <math>5 \times 10^8</math> Inf.U per 0.5 mL.
 
In total 400 subjects will be recruited into this trial. Subjects will receive two administrations 4 weeks apart which will consist of MVA-BN-RSV Dose 1 (<math>1 \times 10^8</math> Inf.U), MVA-BN-RSV Dose 2 (<math>5 \times 10^8</math> Inf.U) or Placebo (TBS). To obtain Dose 1 the MVA-BN- RSV vaccine will be diluted in MVA-BN formulation buffer (TBS) according to the study specific administration instructions. Following the main trial, two subgroups will be identified, which will continue in the booster substudy. The selection is based on safety and immunogenicity data obtained in the main trial.
 
86 subjects from 2 treatment groups (43 per treatment group) are supposed to receive one (booster) dose of MVA-BN-RSV vaccine approximately one year after their first vaccination. In this booster substudy, eligible subjects will receive the same dose they received during the main trial.

For details on the treatment groups see [Table 1](#)

Route of administration	MVA-BN-RSV vaccine/TBS is administered intramuscularly (IM) into the deltoid muscle of the upper arm (preferably the non-dominant arm).
Trial duration	Up to 39 weeks per subject in the main trial and up to additional 56 weeks per subject enrolled in the booster substudy.
Sample size main trial	A total of 400 subjects will be recruited into 5 treatment groups à 80 subjects. PBMC collection will be performed in a subgroup of 20 subjects in each treatment group (total of 100 subjects). This subgroup will also have an additional serum and nasal swab sample collection time point one week post each vaccination in addition to the serum and nasal swab sample collection time points scheduled for all subjects.

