In this RSV trial (RSV-MVA-002) different doses and schedules will be evaluated: all subjects will receive two vaccinations - either both vaccinations with MVA-BN-RSV vaccine  $1 \times 10^8$  Inf.U per 0.5 mL,  $5 \times 10^8$  Inf.U per 0.5 mL or Placebo or the first vaccination with MVA-BN-RSV vaccine  $1 \times 10^8$  Inf.U or  $5 \times 10^8$  Inf.U per 0.5 mL followed by the second vaccination with Placebo (see [Table 1](#)). Please note that the dose was expressed as TCID50 for the Phase I clinical trial with  $1 \times 10^8$  TCID50 per dose corresponding to  $1 \times 10^8$  Inf.U per dose.

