### **3.5.8 Adverse Events**

A summary table by vaccination period and Overall will be presented as an overview of local and general solicited AEs and unsolicited AEs. This summary table will present the number and percentage of subjects who had at least one event in each period as well as the corresponding total number of events for:

- At least one AE documented
- Any TEAE
- Non-serious TEAEs
- SAEs
- Related TEAEs
- TEAEs Graded  $\geq 2$
- TEAEs Graded  $\geq 3$
- Related TEAEs Graded  $\geq 3$

- Related SAEs
- AEs leading to withdrawal from the trial
- AEs leading to withdrawal from second vaccination
- Deaths

The Overall summary is the sum of Period 1 and Period 2 counts.

A similar per subject table will be presented where each subject is counted once per their entire study participation.

For the ATP and FU Phase, all AEs will be listed by subject, including SOC and PT for the FAS. Any AE with onset later than 28 days since the previous vaccination will not be included in summary tables but will be included in the listing and will be flagged accordingly as non-treatment-emergent.

According to the clinical trial protocol no new AEs should be reported during the FU Phase, except SAEs and AEs related to respiratory tract infections, but if any are reported then they will be listed but considered non-treatment-emergent and no statistical testing or summaries will be presented for them.

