### **Solicited Local Adverse Events**

Solicited local AEs will be summarized by PT after each vaccination, and broken down by maximum intensity. The incidence (i.e., the number of subjects developing a specified solicited local AE on the day of vaccination or over the seven days after each vaccination divided by the number of subjects per respective vaccination period) will be calculated. The incidence will also be calculated for any solicited local AE for each vaccination period, the overall vaccination period, by treatment and by age group. The incidence of Grade 2 or higher AEs will also be calculated as well as the incidence of Grade 3 or higher AEs.

The duration (in days) of the solicited local AEs will be summarized and presented in a listing. A similar table and listing will be presented for relative day of onset for solicited local AEs.

Study specific version: 1.0  
Study specific version Date: 31-May-17

All tables created for solicited local adverse events per vaccination period will be repeated but on a per subject basis, where subjects are counted once per each adverse event experienced.

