## 2 Trial Overview

### 2.1 Trial Description

This is a randomized, single-blind, placebo-controlled, dose-ranging Phase II trial in  $\geq 55$  year old adults to evaluate the safety and immunogenicity of the recombinant MVA-BN-RSV vaccine. A total of 420 subjects were recruited into five treatment groups and were vaccinated in the main study (see Table 2).

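### Main-trial safety tables are cut only by the five regimens, so each dose's identical first injection is split over two groups and no dose-level safety estimate is planned

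*SAP*

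**What the plan says.** The main SAP sets the layout in Section 3.5.1: "All tables will be presented by treatment groups". The only further cut mentioned there for safety is by age group, for solicited events.

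Section 3.5.8 presents adverse events by vaccination period. For solicited local events, "Solicited local AEs will be summarized by PT after each vaccination, and broken down by maximum intensity", with incidence "divided by the number of subjects per respective vaccination period". It continues: "The incidence will also be calculated for any solicited local AE for each vaccination period, the overall vaccination period, by treatment and by age group". Solicited general events follow the same pattern. The overview is described as follows: "A summary table by vaccination period and Overall will be presented as an overview of local and general solicited AEs and unsolicited AEs". The same section defines Overall in that overview by adding the counts of the two periods, and a companion table counts each subject once. Appendix 1 (tables 14.3.1.x to 14.3.3.x) offers per-period, per-subject and age-group versions, and none by injection received. Confidence intervals are specified for immunogenicity (Section 3.5.7) and for no safety rate.

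On design, SAP Table 2 gives Groups 1 and 2 the same first dose and Groups 3 and 4 the same first dose. In Groups 1 and 3 the active injection is "followed by the second vaccination with Placebo" (Protocol 2.5.3).

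**The concern.** The two schedules at each dose differ only from the second injection onward. Everything recorded before it (solicited events on Days 0 to 7, unsolicited events in Period 1, and the Visit 2 laboratory values at 12 to 16 days) describes one injection of one dose, in about twice as many subjects as any single column holds. With regimens as the only columns, the reader gets two separate, noisier estimates of the same quantity and no planned comparison of the doses.

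This matters because the trial is dose-ranging and Protocol 2.7 says the main trial evaluates different doses for both immunogenicity and safety. The SAP already uses the structure for titers: the exploratory ANOVA in Section 3.5.7 fits dose and number of vaccinations as separate factors. Safety has no counterpart.

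**Working it through.** **The plan's own figure.** No precision target for safety is stated. The only main-trial calculation is for titers (SAP 3.1): SD 0.46, 66% increase, 80% power, with 5% two-sided assumed here. n = 2(1.960 + 0.842)^2 x 0.46^2 / (log10 1.66)^2 = 68.6, so 69 per group (69.5 with the t distribution, so 70). Then 70/0.88 = 79.5, so 80 recruited. The figure reproduces.

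**Inputs.**
- Planned size: "A total of 400 subjects will be recruited into 5 treatment groups" of 80 each (Protocol 1.5).
- Actual size: "A total of 420 subjects were recruited into five treatment groups and were vaccinated in the main study" (booster SAP 2.1). Its Table 2 gives 78, 89, 80, 90 and 83 for Groups 1 to 5.
- First injection at Dose 1: 78 + 89 = 167. At Dose 2: 80 + 90 = 170.
- Event rates of 30% and 10%, the same in both arms, are assumptions chosen to show a range.

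**Dose 2 minus Dose 1 after injection 1.** 95% half-width = 1.96 x sqrt[p(1-p)(1/n1 + 1/n2)].

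| Comparison | n | 1/n1 + 1/n2 | p = 30% | p = 10% |
|---|---|---|---|---|
| Group 3 v 1 | 80 v 78 | 0.02532 | 14.3 points | 9.4 points |
| Group 4 v 2 | 90 v 89 | 0.02235 | 13.4 points | 8.8 points |
| Pooled | 170 v 167 | 0.01187 | 9.8 points | 6.4 points |

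For example, 1.96 x sqrt(0.21 x 0.01187) = 0.098. At the planned sizes (80 v 80 against 160 v 160) the figures are 14.2 against 10.0 points at 30%, and 9.3 against 6.6 at 10%. The ratio is sqrt(2).

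**Zero events.** Exact two-sided upper 95% limit = 1 - 0.025^(1/n):
- n = 78: 4.6%
- n = 80: 4.5%
- n = 89: 4.1%
- n = 90: 4.0%
- n = 167: 2.2%
- n = 170: 2.1%

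**Dose minus placebo.** The gain is smaller because placebo stays at 83. At 30%, Group 1 v 5 gives 1.96 x sqrt[0.21(1/78 + 1/83)] = 14.2 points and Group 2 v 5 (89 v 83) gives 13.7, against 12.1 for 167 v 83. For Dose 2, Group 3 v 5 (80 v 83) gives 14.1 and Group 4 v 5 (90 v 83) gives 13.7, against 12.0 for 170 v 83.

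**Staggering subjects.** The sentinel and safety cohorts put 1 + 5 = 6 subjects into each of Groups 2 and 4 (SAP 1.1). Assuming they are counted in the 89 and 90, removing them leaves 161 v 164. The pooled half-width at 30% is then 1.96 x sqrt[0.21(1/161 + 1/164)] = 10.0 points, so the gain does not depend on them.

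**Overall column.** In the overview it adds Period 1 and Period 2 counts, with no stated denominator. Solicited incidence for the overall vaccination period has none either. In Groups 1 and 3 the column combines one vaccine injection with one TBS injection. Divided by injections, it would be an average of the two rates. Divided by subjects, it cannot fall below the Period 1 rate, because Period 2 events are added to it. On neither reading is it the rate for one vaccine injection.

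**The case against.** The case for leaving the plan alone is substantial.

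- **Nothing is lost or distorted.** Period 1 columns are shown separately and laboratory values by visit, so anyone can add the counts for Groups 1 and 2 or Groups 3 and 4. This stands, and it limits the point to precision and presentation. Adding counts by hand still supplies no prespecified contrast or interval.
- **No target is missed.** A reader might infer that safety by dose is a secondary objective. The documents do not say so: the objective is the safety and reactogenicity of the vaccine, and the dose-and-schedule objective is framed in terms of immunogenicity. The interest in dose rests on Protocol 2.7.
- **The booster choice was between regimens.** The substudy was added in July 2017, after this SAP, so regimen tables are a natural basis for that decision. This also stands. The groups chosen were 1 and 3, however, and first-injection data from Groups 2 and 4 bear on the same two doses.
- **The Overall column.** A reader might infer that it makes a vaccine injection look milder in Groups 1 and 3. That would need injections as the denominator, which the SAP does not state. The solicited incidence it defines per period uses subjects. What stands is that the denominator is undefined.
- **Pooling has a cost.** The 12 staggering subjects are in Groups 2 and 4 only, in the younger stratum, at one site, with no concurrent placebo. They split 6 and 6 between the doses, so they matter mainly for dose minus placebo. The fix has to deal with them.

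**Conclusion.** The point holds as an inefficiency that is cheap to repair, and it is not a source of bias. In the main SAP provided, no dose-level safety estimate or interval is planned, although the first-injection data would support one. Pooling narrows the Dose 2 minus Dose 1 interval from 13.4-14.3 to 9.8 points at a 30% rate and from 8.8-9.4 to 6.4 at 10%. It lowers the zero-event upper limit from 4.0-4.6% to about 2.2%.

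These figures rest on the vaccinated numbers in the booster SAP, on the assumed event rates, and on every vaccinated subject contributing first-period data. A reader might infer that the comparison was never planned at all. That cannot be confirmed, because the booster SAP cites a main-study SAP Addendum of October 11, 2017 that is not among the documents. The undefined denominator of the Overall column is a separate, smaller gap.

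**What to change.** Keep all regimen tables and add the following.

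1. Period 1 versions of the overview, solicited local, solicited general and unsolicited event tables, and of the Visit 2 laboratory tables, with three columns by injection received: Dose 1 (Groups 1+2), Dose 2 (Groups 3+4) and placebo (Group 5).
2. For a few headline outcomes (any solicited local event, any solicited general event, any Grade 3 or higher event, any related event), Dose 2 minus Dose 1 and each dose minus placebo with 95% confidence intervals, labelled descriptive.
3. Stratification of these contrasts by age group, or a second version without the 12 staggering subjects.
4. A stated denominator for every Overall column, with vaccine and TBS injections shown separately for Groups 1 and 3.

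No new data are needed. The cost is a longer table set and up to 4 x 3 = 12 additional unadjusted descriptive contrasts.
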